**C.4.19.3 Inference on DCM model structure:** In DCM analysis, the number of candidate DCMs, after permutation and combination of possible endogenous connections and exogenous inputs, is very large. Therefore, the network discovery technique (NDT) [189], as implemented in the latest release of DCM, is used as a first step to determine the model structure for each subject. The NDT scores the relative posterior probability of each candidate DCM in order to evaluate efficiently the large number of possible DCMs and to find the optimal model for each subject. The initial full model to be reduced by NDT includes all possible bi-directional endogenous connections between each node (see C.4.19.1 and C.4.19.2 VOIs). The contextual conditions of the cognitive tasks are putative exogenous inputs and bilinear modulators at each connection in the initial full model. In addition, nonlinear gating by dorsal striatum on PFC-PPC is hypothesized in the initial full model (see section C.4.19.1 and C.19.2). The NDT results for each subject are checked first to see

whether the causal (directional) relationship between the OLPFC and the striatum has been determined and whether the striatal gating OCM is optimal for all subjects in each group. The inference on model structure is further conducted using Bayesian model selection (BMS) [190] and Bayesian family level inference (BFLI) [191], as described in detail in Ma, et al. [138]. BMS is an established procedure for selecting an optimal OCM from alternative OCMs. This is realized by comparing model evidence, which simultaneously quantifies how accurately a model explains the data and model complexity [190]. An "optimal" model is reflected by the Bayesian exceedance probability [190], which denotes the probability that a model is more likely to have generated the observed data than the other models considered. BFLI is an extension of BMS that can be used to select the optimal family from candidate families of models [138, 191].

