**C.4.19.4 Inference on DCM parameters:** The inference on OCM parameters is conducted using Bayesian model averaging (BMA) [191]. BMA is a Bayesian approach that averages each OCM parameter across subjects and across models such that the contribution of each model (of each subject) for that parameter is weighted by each model's posterior probability for that subject. Thus, BMA avoids the rigid assumption of an identical single OCM for all subjects that is required in classical "Frequentist" analysis of OCM parameters [191]. The same model space, comprised of the optimal OCM for the COs group plus the optimal OCM for the control group, is used in the BMA analysis of each group to determine the posterior distribution of each OCM parameter for each subject within the group [138].

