Urn randomization [153], a form of stratified randomization, will help ensure comparability of treatment groups on baseline severity and duration of cocaine abuse. Pretreatment task behavioral performance or demographic variables on which group differences are detected, and which are correlated with outcomes, meet the definition of confounders [192, 193]. In such cases, analyses will evaluate the robustness of findings after statistically controlling for the confounder. If conclusions remain unchanged after covarying for the confounder, the more parsimonious model will be reported along with a statement indicating its robustness to covariation for potential confounding. If inclusion of the covariate alters the conclusions of the analysis, both models will be reported. Treatment success is a function of two elements: (a) retention and (b) demonstrating cocaine-free status using the SRPHK1 criteria (see section C.3.4). The Treatment Effectiveness Score (TES) provides a metric for this composite outcome [194]. TES is the sum of all cocaine-negative tests (according to SRPHK1 rules). Higher TES indicates that participants both continue to participate in the study and are negative for cocaine. For each group, BMA (section C.4.19.4) is conducted across all OCMs in the model space. Group difference in the gating effect by the dorsal striatum is assessed using Bayesian confidence probability [195]. In addition, BMA is conducted across all OCMs in the model space for each subject in the medication group and in the placebo group. Evaluation of differential treatment response, measured by the TES, as a function of the averaged (across the OCM model space) gating effect, will use Poisson regression. Violations of assumptions of dispersion will result in the use of more appropriate approaches such as zero-inflated Poisson, negative binomial, or zero-inflated negative binomial models. Regression of treatment, averaged gating, and their interaction will permit evaluation of differential treatment response as function of gating. The critical element in doing so is the evaluation of the interaction term. Given that the current study is powered to detect group differences, it is likely underpowered to detect an interaction. Brookes, et al. [196] demonstrate that for studies with 80% power to detect a between-groups effect, power to detect an interaction effect of the same magnitude as the main effect is approximately 29%. One solution is to adopt a Bayesian subgroup analysis approach [197-201]. This approach utilizes the posterior distribution of the interaction parameter to estimate the

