Urn randomization, a form of stratified randomization, will help ensure comparability of treatment groups on baseline severity and duration of cocaine abuse. Pretreatment task behavioral performance or demographic variables on which group differences are detected, and which are correlated with outcomes, meet the definition of confounders. In such cases, analyses will evaluate the robustness of findings after statistically controlling for the confounder. If conclusions remain unchanged after covarying for the confounder, the more parsimonious model will be reported along with a statement indicating its robustness to covariation for potential confounding. If inclusion of the covariate alters the conclusions of the analysis, both models will be reported. Treatment success is a function of two elements: (a) retention and (b) demonstrating cocaine-free status using the SRPHK1 criteria. The Treatment Effectiveness Score (TES) provides a metric for this composite outcome. TES is the sum of all cocaine-negative tests (according to SRPHK1 rules). Higher TES indicates that participants both continue to participate in the study and are negative for cocaine. For each group, BMA is conducted across all DCMs in the model space. Group difference in the gating effect by the dorsal striatum is assessed using Bayesian confidence probability. In addition, BMA is conducted across all DCMs in the model space for each subject in the medication group and in the placebo group. Evaluation of differential treatment response, measured by the TES, as a function of the averaged (across the DCM model space) gating effect, will use Poisson regression. Violations of assumptions of dispersion will result in the use of more appropriate approaches such as zero-inflated Poisson, negative binomial, or zero-inflated negative binomial models. Regression of treatment, averaged gating, and their interaction will permit evaluation of differential treatment response as function of gating. The critical element in doing so is the evaluation of the interaction term. Given that the current study is powered to detect group differences, it is likely underpowered to detect an interaction. Brookes, et al. demonstrate that for studies with 80% power to detect a between-groups effect, power to detect an interaction effect of the same magnitude as the main effect is approximately 29%. One solution is to adopt a Bayesian subgroup analysis approach. This approach utilizes the posterior distribution of the interaction parameter to estimate the probability that it exceeds some number (e.g., for Poisson regression a Risk Ratio of 1.0). Specification of vague neutral priors will reflect uncertainty regarding parameter values, utilizing prior distributions for the lower order effects that are neutral and diffuse with specification  $\sim N(0, 1 \times 10^{-6})$  on the log scale (i.e., centered at the null hypothesis with a 95% Credible Interval of  $\pm 1960$ ) for all coefficients, and  $\sim U(0, 100)$  for any required dispersion terms. Examination of the interaction of treatment and the subgroup index forms the crux of the evaluation of the subgroup effect. For evaluating the interaction representing the differential subgroup effect, analysis will be conducted in two ways: (a) utilizing diffuse, indifferent priors ( $\sim N(0, 1 \times 10^{-6})$ ) on the log scale for the interaction coefficients, and (b) using informative skeptical priors for the coefficients will evaluate sensitivity of statistical conclusions to specification of priors. Informative, skeptical priors will be derived via the method first proposed by Dixon and Simon. Evaluation of resulting posterior distributions will permit conclusions regarding the probability that subgroup/interaction effects of varying magnitudes obtain. Examples of this use of the posterior distribution may be found in Green et al. (2009). Bayesian modeling will use SAS v9.2 (Proc Genmod and Proc Monte-Carlo Markov chain [MCMC]), and in WinBugs 1.4.3 (<http://www.mrc-bsu.cam.ac.uk/bugs>). Convergence of Bayesian analyses on the posterior distributions via MCMC will be assessed via graphical (Trace Plot, Autocorrelation Plot) and quantitative (Geweke Diagnostics, Gelman-Rubin Diagnostics, and Heidelberger-Welsh Diagnostics) evidence. Evaluation of posterior distributions will permit statements regarding the probability that effects of varying magnitudes exist, given the data.

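### The plan does not ensure that the models averaged to give each patient's gating value, the Aim 2 and 3 predictor, contain the gating term

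*Protocol*

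**What the plan says.** The gating predictor is built in four steps.

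- **Starting model.** Protocol C.4.19.3 begins from a full model: "The initial full model to be reduced by NDT includes all possible bi-directional endogenous connections between each node". It adds that "nonlinear gating by dorsal striatum on PFC-PPC is hypothesized in the initial full model". (The extracted text prints DCM as OCM and CDs as COs in places.)
- **Selection.** The network discovery results are checked for whether the gating DCM is optimal for all subjects in each group. Bayesian model selection and family-level inference follow. No consequence is given if the check fails.
- **Averaging.** C.4.19.4 defines the averaging set: "The same model space, comprised of the optimal OCM for the COs group plus the optimal OCM for the control group". Each model's contribution is "weighted by each model's posterior probability for that subject".
- **Use.** Under Specific Aim 2, C.4.20 says "BMA is conducted across all OCMs in the model space for each subject in the medication group and in the placebo group". Treatment response is then evaluated "as a function of the averaged (across the OCM model space) gating effect, will use Poisson regression". On the treatment-by-gating product it says: "The critical element in doing so is the evaluation of the interaction term".

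The SAP's Data analysis plan repeats the use step ("as a function of the averaged (across the DCM model space) gating effect, will use Poisson regression") but does not define the model space. C.4.20 describes the Aim 3 analysis as essentially the same as for Aims 1 and 2, so response inhibition inherits the rule.

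**The concern.** Aim 2 needs a graded gating value for every medicated and placebo patient. The plan secures the gating term at the start of the modelling and uses it at the end, but nothing in between keeps it. The set averaged holds two models, each chosen because it is the optimum for a whole group, and neither has to contain the parameter that becomes the predictor. The plan also does not say what value a patient receives from a model without the term.

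At stake is the test that C.4.20 calls critical. The same section concedes that the interaction is probably underpowered, so avoidable error in the predictor is costly. If the rule is settled only after the model selection results are known, the choice of predictor also becomes post hoc.

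**Working it through.** **1. The plan's own figure.** C.4.21 gives an effect of 0.60 (labelled d, used as a correlation), n = 24, two-sided alpha 0.05 and power 86%.

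Power = Φ(atanh(r) × √((n − 3)/v) − 1.960), with atanh(0.60) = 0.693 and √21 = 4.583.

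- Pearson, v = 1: 3.176 − 1.960 = 1.216, giving 88.8%.
- Spearman, v = 1.06: 3.085 − 1.960 = 1.125, giving 87.0%. A rank-based simulation (50,000 runs) gives 85.1%.

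The 86% is reproduced on a Spearman basis, which is the method of the pilot in C.2.4. It presumes a directly measured gating value in each of 24 subjects.

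**2. The three possible outcomes of selection.** Let θ be a patient's gating estimate under a model with the term, and w that model's posterior probability for the patient. Assume that an absent term counts as zero; the plan does not say.

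| Optimal models with gating | Patient's value | Consequence |
|---|---|---|
| Both | weighted mean of two gating estimates | no problem |
| One | w × θ | scaled by a weight that depends on every difference between the two networks |
| Neither | 0 for all | interaction not estimable |

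In the last row, with 24 medicated and 24 placebo patients, the columns are intercept, treatment, gating and treatment × gating. The last two are all zero, so the matrix has rank 2 of 4. Under the diffuse prior centred at zero, the posterior for the interaction is the prior, and P(risk ratio > 1) = 0.5. The software would still return a number, but it would carry no information from the data.

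**3. Illustration of the one-model case.** The documents give no distribution for θ or w. Assume θ has SD 1 and mean μ, correlates 0.60 with outcome, and is independent of w, which is also independent of outcome. Then

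corr(wθ, outcome) = 0.60 × E(w) / √(E(w²)(1 + μ²) − E(w)²μ²).

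Example, w uniform on 0 to 1:

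- μ = 0: 0.30/√(1/3) = 0.52
- μ = 2: 0.30/√(5/3 − 1) = 0.37

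| Assumed w | Correlation, μ = 0 | Power | Correlation, μ = 2 | Power |
|---|---|---|---|---|
| Always 1 | 0.60 | 89% | 0.60 | 89% |
| Beta(5,5) | 0.57 | 85% | 0.50 | 70% |
| Uniform | 0.52 | 75% | 0.37 | 42% |
| Beta(0.2,0.2) | 0.46 | 62% | 0.28 | 26% |
| Beta(0.5,2) | 0.41 | 52% | 0.23 | 19% |

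Power is by the Pearson formula at n = 24, so the comparator is 88.8%, not 86%. The share of the predictor's variance linearly explained by w alone runs from 0% to 68%.

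**4. A second illustration, with w depending on gating.** Assume true gating has SD 1, estimation error has SD 0.5 or 1, and only the control-group optimum contains gating. Assume further that the other connections shift the log evidence for that model by a mean of 0 to −6 with SD 3 to 6. The correlation of the averaged value with true gating falls from 0.89 to 0.63–0.85 (error SD 0.5) and from 0.71 to 0.35–0.61 (error SD 1). Rank correlations fall less, to 0.72–0.85 and 0.48–0.63. If the two models differ only in the gating term, the loss is negligible (0.89 to 0.88).

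**The case against.** The best reply is that the documents never show gating being removed. C.4.19.3 describes the candidates as arising from endogenous connections and exogenous inputs, and adds gating separately. The only selection contrast spelled out in C.4.20 and the SAP is the direction of the link between DLPFC and ventral striatum. C.4.19.1 and C.4.19.2 each specify a striatal gating DCM. The pilot in C.2.4 built gating in by hypothesis and obtained a correlation with outcome. On that reading every candidate keeps the term. The protocol also refers to a cited methods paper for detail, which was not available for this review.

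This stands as far as it goes: loss of gating is possible, not demonstrated. But C.4.19.3 itself checks whether the gating DCM is optimal, which treats the matter as open, and gives no rule for a negative answer. The definition of a key predictor should not depend on which reading is right.

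A reader might infer that the term is dropped precisely in low-gating patients, those of most interest. The documents do not support that. The averaging set comes from group optima, not from each patient's own reduced model, and C.2.4 describes heterogeneity in dorsal striatum among cocaine-dependent subjects. A patient with little true gating who receives a value near zero is not misranked either. The damage would come from patients with appreciable gating whose values are shrunk by unrelated fit.

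**Conclusion.** The gap is real and conditional. As written, the rule can produce a constant predictor, which makes the treatment-by-gating interaction inestimable. It can also produce a predictor partly scaled by fit unrelated to gating. It is harmless if both group optima contain the term, and the plan does not guarantee that.

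The inestimable case follows from the design matrix once an absent term is counted as zero. The losses in the one-model case rest on assumed gating distributions, estimation errors and model weights. They do not indicate likely size, and the documents do not allow one to be derived.

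Two further inferences should be resisted. The 86% power figure is not wrong on its own inputs. Nor does this working say anything about the Aim 1 connection from DLPFC to ventral striatum, which it did not examine.

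**What to change.** In C.4.19.4, C.4.20 and the SAP, define the model space for the Aim 2 and Aim 3 regressor so that every model averaged contains the dorsal-striatal gating term. That is per-subject Bayesian model averaging within the gating family. Report the gating versus no-gating family probability separately, as evidence on whether gating exists. Keep the planned two-model value as a sensitivity analysis, stating what value an absent term takes.

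Forcing one fixed DCM on everyone is not the better lead remedy. C.4.19.4 chose averaging in order to avoid assuming an identical model for all subjects, and averaging within the gating family preserves that.

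The cost is a change of wording and some extra model estimation on data already planned. Values will be noisier in subjects whose data favour no gating.

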**C.4.20 Statistical analysis:**

**Specific Aim 1:** To conduct an snOCM study of working memory to determine the baseline effective connectivity between OLPFC and striatum in treatment-seeking COs compared to non-drug using controls.

Initial analyses will evaluate group differences on demographic and baseline variables, will use contingency tables with chi-square testing, ANOVA's, and examination of correlations between baseline variables and snOCM results. The Friston et al. [189] network discovery technique, BMS, and BFLI (C.4.19.3) will be used to select the optimal model based on the exceedance probability of the OCM (or family of OCMs) in which OLPFC causally affects ventral striatum vs. exceedance probability of the OCM (or a family of OCMs) in which the ventral striatum causally affects the OLPFC. The parameter estimates for the endogenous OLPFC-striatal connectivity will be compared between groups using BMA and also compared using analysis of covariance.

**Specific Aim 2:** To determine whether the pretreatment gating effect by dorsal striatum on IFC-PPC effective connectivity (reflecting low OA) predicts treatment response to OA pharmacotherapy in COs.

Urn randomization [153], a form of stratified randomization, will help ensure comparability of treatment groups on baseline severity and duration of cocaine abuse. Pretreatment task behavioral performance or demographic variables on which group differences are detected, and which are correlated with outcomes, meet the definition of confounders [192, 193]. In such cases, analyses will evaluate the robustness of findings after statistically controlling for the confounder. If conclusions remain unchanged after covarying for the confounder, the more parsimonious model will be reported along with a statement indicating its robustness to covariation for potential confounding. If inclusion of the covariate alters the conclusions of the analysis, both models will be reported. Treatment success is a function of two elements: (a) retention and (b) demonstrating cocaine-free status using the SRPHK1 criteria (see section C.3.4). The Treatment Effectiveness Score (TES) provides a metric for this composite outcome [194]. TES is the sum of all cocaine-negative tests (according to SRPHK1 rules). Higher TES indicates that participants both continue to participate in the study and are negative for cocaine. For each group, BMA (section C.4.19.4) is conducted across all OCMs in the model space. Group difference in the gating effect by the dorsal striatum is assessed using Bayesian confidence probability [195]. In addition, BMA is conducted across all OCMs in the model space for each subject in the medication group and in the placebo group. Evaluation of differential treatment response, measured by the TES, as a function of the averaged (across the OCM model space) gating effect, will use Poisson regression. Violations of assumptions of dispersion will result in the use of more appropriate approaches such as zero-inflated Poisson, negative binomial, or zero-inflated negative binomial models. Regression of treatment, averaged gating, and their interaction will permit evaluation of differential treatment response as function of gating. The critical element in doing so is the evaluation of the interaction term. Given that the current study is powered to detect group differences, it is likely underpowered to detect an interaction. Brookes, et al. [196] demonstrate that for studies with 80% power to detect a between-groups effect, power to detect an interaction effect of the same magnitude as the main effect is approximately 29%. One solution is to adopt a Bayesian subgroup analysis approach [197-201]. This approach utilizes the posterior distribution of the interaction parameter to estimate the

probability that it exceeds some number (e.g., for Poisson regression a Risk Ratio of 1.0). Specification of vague neutral priors will reflect uncertainty regarding parameter values, utilizing prior distributions for the lower order effects that are neutral and diffuse with specification  $-N(0, 1 \times 10^{-6})$  on the log scale (i.e., centered at the null hypothesis with a 95% Credible Interval of  $\pm 1960$ ) for all coefficients, and  $-U(0, 100)$  for any required dispersion terms. Examination of the interaction of treatment and the subgroup index forms the crux of the evaluation of the subgroup effect. For evaluating the interaction representing the differential subgroup effect, analysis will be conducted in two ways: (a) utilizing diffuse, indifferent priors  $(-N(0, 1 \times 10^{-6})$  on the log scale for the interaction coefficients, and (b) using informative skeptical priors for the coefficients will evaluate sensitivity of statistical conclusions to specification of priors. Informative, skeptical priors will be derived via the method first proposed by Dixon and Simon [200]. Evaluation of resulting posterior distributions will permit conclusions regarding the probability that subgroup/interaction effects of varying magnitudes obtain. Examples of this use of the posterior distribution may be found in Green et al. [197]. Bayesian modeling will use SAS v9.2 (Proc Genmod and Proc Monte-Carlo Markov chain [MCMC]), and in WinBugs 1.4.3 (<http://www.mrc-bsu.cam.ac.uk/bugs>). Convergence of Bayesian analyses on the posterior distributions via MCMC will be assessed via graphical (Trace Plot, Autocorrelation Plot) and quantitative (Geweke Diagnostics, Gelman-Rubin Diagnostics, and Heidelberger-Welsh Diagnostics) evidence. Evaluation of posterior distributions will permit statements regarding the probability that effects of varying magnitudes exist, given the data.

While the use of urn randomization [153] will likely result in comparable groups, substantial heterogeneity may still exist within conditions on baseline variables such as severity, duration of use, and impulsivity. We propose subgroup analyses following the procedures described above. This will determine the degree to which baseline variables moderate the interaction of treatment and snOCM.

Specific Aim 3: To conduct an snOCM of impulsivity to test Hypotheses 1 and 2 (above).

The statistical analysis is essentially the same as in Specific Aims 1 and 2.

C.4.21 Power Analysis: The power analysis was conducted using StudySize 2.0 software

(<http://www.studysize.com/>). The power analysis for the correlation analysis between the DCM striatal gating effect and the subsequent treatment outcome (Specific Aim 2) is based on the preliminary data (Section C.2.4). We have shown an effect size of 0.69 in our correlation analysis, but this is probably inflated due to the small sample size. Therefore we have conservatively used a more modest effect size of 0.60 when calculating the power. For an effect size  $d = 0.60$  and 2-tailed alpha = 0.05, a sample size of 24 subjects would achieve a power of 86% for the correlation analysis. For Specific Aim 1, our pilot data (Section C.2.4) showed an effect size of 1.89 for the between-group comparison of the strength of the endogenous connection from DLPFC to ventral striatum. Based on this effect size, we have calculated that 24 subjects per group would achieve a power of 99.9% at a 2-tail alpha = 0.05. Previous studies by our group [35, 37] (section C.2) found significant fMRI activation in predicted regions with 19 CDs and 14 controls. Thus we expect significant fMRI activation in the current project using the same fMRI task and scanning parameters with 24 subjects per group.

C.4.22 Limitations: OCM is based on several assumptions, especially in its original form [75]. However, we will use the OCM extensions, nonlinear [76] and stochastic [77] OCM, to reduce the dependence on these assumptions. OCM is a relatively new approach to study effective connectivity. However, OCM is being established as a primary effective connectivity technique in the neuroimaging literature, as evidenced by rapidly increased citation rates [78], overall publication number [203], and publication number in other patient populations [79], and high reliability has been shown in healthy subjects [80]. This project will only study COs who are treatment-seeking individuals, which may affect generalization of the findings to all COs. We believe that this is an acceptable trade-off because the major objective of this study is to develop a novel biomarker to predict treatment response in treatment-seeking COs.

1. Be between 18 and 50 years of age;
2. Right handed;
3. Have no past history of Psychiatric or non-Psychiatric medical disorders which could affect the central nervous system as assessed by SCID and physical examination.
4. Be in acceptable health on the basis of interview, medical history, labs, and physical exam;
5. Be able to understand the consent form and provide written informed consent;
6. Have a medical history and physical examination demonstrating no clinically significant contraindications for study participation;
7. Have no metal fragments or other bodily metal (pacemaker) or significant claustrophobia that would put the subjects at risk for MRI scanning.

Cocaine-dependent subjects with medical conditions contraindicated to, or taking medications known to have significant drug interactions with the study medication(s) will be excluded from the ongoing clinical trial, and therefore will not participate this study. In addition, a subject will be excluded from this study if any of the following conditions apply:

1. Current DSM-IV diagnosis of any psychoactive substance dependence other than cocaine, marijuana, or nicotine (for cocaine-dependent subjects only);
2. Current DSM-IV diagnosis of any psychoactive substance dependence (for non-drug using control subjects only);
3. Have a DSM-IV axis I psychiatric disorder (other than psychoactive substance abuse or dependence as described in criteria 1 for cocaine dependent subjects) or neurological disease or disorder;;
4. Have cognitive impairment due to non-substance related factors (e.g., history of stroke, transient ischemic attacks, mental retardation, epilepsy, head injury);
5. Significant current suicidal or homicidal ideation;
6. Take CNS active concomitant medications;
7. Pregnant or nursing (for female subjects only);
8. Inability to read, write, or speak English;
9. Unwillingness to sign a written informed consent form;
10. Have evidence of clinically significant heart disease or hypertension.

